6.2. Registration

This is a single center trial conducted at The Ohio State University (OSU). [name] [name], the lead clinical investigator, will coordinate protocol management with

assistance from Drs. [name] and [name], who will also have access to and responsibility for regulatory matters. All patients for whom questions arise relative to eligibility for the study should be discussed with one of the principal investigators prior to entry onto the study.

Patients will be registered by a clinical research coordinator, as per CTO standard practice. Because of the highly infectious nature of COVID-19 and need to conserve personal protective equipment, the study will be discussed with the patient by a study PI or co-I through a video or telephone conference, prior to the research coordinator initiating the consent process. It is expected that most study laboratories will be available from standard of care procedures prior to study enrollment, and these can be used for screening studies as long as they are obtained within 3 days of screening. Patients with a positive SARS-CoV-2 PCR result performed at any facility within 10 days of screening do not need to be retested given the known prolonged shedding nature of the viral infection.

Patients will be registered after meeting all entry requirements, clearance by the Protocol Coordinator, and signing of the informed consent.

Following registration, patients should begin protocol treatment within 48 hours. Issues that would cause treatment delays should be discussed with the Principal Investigator as soon as possible.

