7.1.2 Randomized Double-Blind Phase 2 Study

In the phase 2 portion of the study, patients will be randomized in a 1:1 fashion to receive ibrutinib plus standard care for COVID-19 versus placebo plus standard treatment for COVID-19. The study is double blinded and each patient will be assigned a randomization number by the James blind pharmacy. The patient, treating physicians, study personnel, and outcome assessors will all remain blinded to group assignment until after the database is locked and blinded analysis is completed. Only the unblinded statistician and the pharmacy staff have access to the unblinded randomization list.

Patients may receive any additional therapies that are not prohibited in the section on concomitant medications. In this trial, cycles will be 7 days in length. Ibrutinib therapy will continue for 2 cycles (14 days). Dose of study drug should be held or modified for adverse events as outlined in **Section 7**.

Patients who develop respiratory failure but are determined by the principal investigator to have clinical benefit from treatment may continue on for the full course of treatment.

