9.9. Data and Safety Monitoring

Ibrutinib for COVID 19

This study will be monitored both by the investigators and The OSU Data and Safety Monitoring Committee (DSMC), a multidisciplinary board that will monitor the safety and conduct of this trial to ensure patient safety, data quality, and data timeliness. The outcome of the DSMC review of the Lead-in component of the study will be shared with PCYC/Janssen.

The OSU Comprehensive Cancer Center DSMC is composed of a multidisciplinary team with expertise reviewing clinical trial data and adverse events. Information to be provided to the committee may include: up-to-date participant accrual; dosing information; all grade 2 or higher adverse events that have been reported across all sites as well as a summary of all deaths occurring within 30 days of the last day of the treatment period. In addition to safety results, all response/efficacy information (including laboratory results, scans etc.) will be reviewed to better assess the risk/benefit of the study intervention. Should any major concerns arise, the DSMC, after meeting in a closed session, will offer recommendations regarding whether or not to suspend or amend the study.

The DSMC will review all serious adverse events in real time. Outside of concerns regarding adverse events (including SAEs reviewed by the DSMC), the DSMC will review safety data at the next DSMC meeting after the first 12 patients have completed therapy and thereafter every time 30 additional patients have completed therapy (e.g. 12 patients, 42 patients, 78 patients) or every 3 months, whichever comes more quickly. .

The study investigators will conduct continuous review of data and will hold weekly teleconferences to discuss toxicities throughout the course of the trial. Any disagreement among the Co-Investigators as to the safety of the trial will be escalated to the DSMC. Frequency and severity of adverse events will be reviewed by the principal investigator and compared to what is known about the agent from other sources; including published literature, and scientific meetings to determine if the trial should be terminated before completion.

All reportable Serious Adverse Events (SAE) will also be reported to the OSU Cancer IRB as per the policies of the IRB.

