Primary Endpoint Analysis: All randomized patients will be included in the primary endpoint analysis and analyzed in the treatment arm to which they were randomized (ITT population). The data will be analyzed using a one-sided Fisher's exact test and a promising signal declared if $p \leq 0.20$ and the event rate is lower in the experimental arm. Since the primary endpoint is to be measured within the first 30 days of registration, we do not expect that primary endpoint information will be missing. However, if there is data missing, the patient will be considered a treatment failure.

Sensitivity analyses include comparison between treatment arm when adjusting for stratification factors and other important variables such as type of cancer or more refined categories of standard of care therapy via logistic regression. If there are events for respiratory failure based on clinical diagnosis without an objective measure and driven solely by resource limitation or if patient has DNI (Do Not Resuscitate) status, a sensitivity analysis will compare arms excluding patients with these events. Sensitivity analyses will be performed for the ITT population and for eligible patients who receive their assigned therapy without a major protocol violation.

Adverse Event Stopping Rules: If there is no concerning safety signal in the lead-in cohort, and the study is able to continue to the randomized component as planned, we have included a plan for comparing toxicity at the interim analyses (first 30 patients across both arms). Accrual will be temporarily suspended to this study and discussion of the data with co-investigators and the data safety monitoring board will occur if we observe adverse events that satisfy the following criteria:

- If the percentage of grade 3/4 all-cause adverse events is at least 15% higher in the ibrutinib arm than in the standard of care arm. This would also include grade 2 hemorrhage if considered significant by the treating physician in collaboration with PI.
- If the percentage of grade 4 all-cause adverse events is at least 15% higher in the ibrutinib arm than in the standard of care arm
- If the percentage of grade 5 treatment-related adverse events is at least 5% higher in the ibrutinib arm than in the standard of care arm

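### The interim adverse event rule takes the data to co-investigators although every criterion is a between-arm difference, so a trigger discloses an ibrutinib excess to people Section 7.1.2 means to keep blinded

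*Combined protocol and SAP*

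**What the plan says.** Section 13 (Adverse Event Stopping Rules) plans for "comparing toxicity at the interim analyses (first 30 patients across both arms"). Accrual is suspended if any of three conditions holds:

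- grade 3/4 events of any cause, with significant grade 2 hemorrhage added, at least 15% more frequent on ibrutinib;
- "If the percentage of grade 4 all-cause adverse events is at least 15% higher in the ibrutinib arm";
- "percentage of grade 5 treatment-related adverse events is at least 5% higher in the ibrutinib arm".

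When that happens, "discussion of the data with co-investigators and the data safety monitoring board will occur if we observe adverse events" of this kind. The sentence does not say who evaluates the criteria or in what form the data are shown.

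Section 7.1.2 says: "The patient, treating physicians, study personnel, and outcome assessors will all remain blinded to group assignment until after the database is locked". It adds: "Only the unblinded statistician and the pharmacy staff have access to the unblinded randomization list". Section 9.9 provides that "the DSMC, after meeting in a closed session, will offer recommendations regarding whether or not to suspend or amend the study". It does not reserve by-arm results for that session, and it also has the investigators review data continuously and discuss toxicities weekly. Section 8.3 deals only with emergency unblinding of single patients.

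**The concern.** A safety rule in a double-blind trial has to be workable without telling blinded staff how the arms compare. Here the people named beside the safety board are co-investigators, and the thing to be discussed is defined by a difference between arms.

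They are not remote from the trial. Section 6.2 says "the study will be discussed with the patient by a study PI or co-I" before consent. Under Section 7.1.2 the principal investigator judges whether a patient with respiratory failure is benefiting and may continue. Under Section 9.6 investigators attribute adverse events to study drug, which feeds the grade 5 criterion. Under Section 13 the principal investigator helps decide which grade 2 hemorrhages count. The primary endpoint includes starting high-flow oxygen or non-invasive ventilation and, in limited circumstances, a clinical diagnosis of respiratory failure.

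Knowing that ibrutinib has the excess could therefore affect recruitment conversations, attribution and, to some degree, endpoint ascertainment for the rest of the trial.

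**Working it through.** **1. The plan's own figure.** The documents give no operating characteristics for the safety rule. The nearest stated figure is the design power of 82.8% (60 patients, 40% vs 15%, one-sided 0.20). Inverting the Casagrande-Pike-Smith correction, n = (n'/4)·(1 + √(1 + 4/(n'd)))² with n = 30 and d = 0.25 gives n' ≈ 22.5 per arm. The pooled z-test then has 86.0% power, and 82.8% once the futility stop at half the information is added. The figure reproduces, and nothing in it depends on who sees safety data.

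**2. What a trigger discloses.** Each criterion has the form (rate on ibrutinib) − (rate on control) ≥ threshold. Being told that one is met tells the listener the sign of the difference and a lower bound on its size. The figures behind it mean nothing without the arms.

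**3. Threshold in patients.** Assumptions: 30 patients at 1:1 give 15 per arm; events are counted by patient; the percentages are read as percentage points.

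- 15 points: 2/15 = 13.3% is too small and 3/15 = 20.0% suffices, so 3 more patients on ibrutinib.
- 5 points: 1/15 = 6.7% suffices, so 1 more patient.

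**4. Chance of a trigger with no true difference.** Let X and Y be independent Binomial(15, p). The chance is P(X − Y ≥ k), summed exactly. The values of p are assumed.

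| Criterion | Common rate p | Chance met |
|---|---|---|
| 15 points (k = 3) | 10% | 6.1% |
| | 20% | 12.5% |
| | 30% | 15.9% |
| | 40% | 17.6% |
| | 50% | 18.1% |
| | 60% | 17.6% |
| Grade 5 (k = 1) | 2% | 20.1% |
| | 5% | 31.6% |
| | 10% | 37.5% |

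These are for each criterion separately. The criteria overlap, so the figures must not be added.

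**5. When individual assignments can be deduced.** Investigators make the attributions, so they know how many treatment-related deaths there are in total. If there is one, the grade 5 criterion can be met only by 1 vs 0, so learning that it was met identifies that patient's arm. More generally, given that it is met, P(Y = 0 | X − Y ≥ 1) = P(X ≥ 1)·P(Y = 0) / P(X − Y ≥ 1). At p = 2%, P(Y = 0) = 0.98¹⁵ = 0.739, giving 0.261 × 0.739 / 0.201 = 96%. At 5% and 10% the result is 79% and 44%. In those cases anyone shown the by-arm counts knows that every treatment-related death was on ibrutinib.

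**6. Patients still to be randomized.** At most 60 − 30 = 30 or 66 − 30 = 36, and at most 120 − 30 = 90 if the sample size goes to its cap. Section 13 times the interim analysis at 30 days of follow-up and states no enrollment pause for the randomized part. Patients entered in that window lower these numbers, and the accrual rate is not given.

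**The case against.** The best defense is that the two sections can be read together. Section 7.1.2 literally protects assignments and the randomization list, not aggregate rates. The unblinded statistician could evaluate the criteria, the DSMC could review by-arm data in closed session, and co-investigators could discuss pooled or case-level data. That by-arm tables go to co-investigators is an inference, since Section 13 says only that the data are discussed.

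Much of this stands. A reader might infer that Sections 7.1.2 and 13 are irreconcilable, or that by-arm tables are certain to reach the clinicians managing patients. The documents support neither. Note A to the Study Calendar lets the inpatient team, who need not be study personnel, do the examinations. Section 13 does not name treating physicians or outcome assessors as recipients. Most endpoint components are delivered interventions, high-flow oxygen has numerical thresholds, and events resting on clinical diagnosis alone already have an exclusion sensitivity analysis.

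What does not stand is that the joint reading removes the problem. The firewall it needs is not written anywhere, and even with pooled tables the fact of a trigger carries the direction of the difference.

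**Conclusion.** The point holds as a conflict with the intent of the blinding section. A stated rule names recipients who should not receive what the rule discloses. A trigger certainly reveals that ibrutinib has the excess, and discussion of the data would probably reveal by-arm rates. Group rates do not generally unblind individuals. The clear exception is the grade 5 criterion when treatment-related deaths are few.

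Release happens only if a criterion is met. With no true difference, that chance is about 6–18% for each 15-point criterion and 20–38% for grade 5, under the assumed rates, 15 per arm and patient-level counting. It is tempting to say that one trial in six would release data by chance, or that half or more of the patients would still be unrandomized. The first holds only for 15-point rates near 30–50%, which the documents do not supply. The second ignores accrual during the 30-day follow-up. Any effect on the primary endpoint is possible but cannot be quantified from the documents.

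**What to change.** In the Adverse Event Stopping Rules, remove co-investigators from the sentence on discussion of the data, and add words to this effect:

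> The unblinded statistician evaluates the adverse event criteria and reports by-arm results only to the DSMC in closed session. Investigators receive the DSMC recommendation and pooled adverse event data. A notice of suspension does not state which criterion was met.

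Add a matching sentence to Section 9.9 so that the closed session is the only place where by-arm safety data are seen. The weekly toxicity calls can continue on pooled data.

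This is a wording change. The unblinded statistician and the closed session already exist, and thresholds, sample size and power stay as they are. There are two small costs. Co-investigators lose by-arm input to the safety discussion. And because every criterion points the same way, a suspension under this rule still hints at an ibrutinib excess. Leaving the criterion unnamed reduces that hint but does not remove it.

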Concern for administering ibrutinib or even more selective BTK inhibitors for the treatment of COVID-19 syndrome includes 1) impairment of humoral or cellular immune

response to SARS-COV-2 virus; 2) overlapping cardiac toxicity that might occur with viral induced cardiac symptoms and also therapeutics such as chloroquine and hydroxychloroquine; 3) increased bleeding given the presence of thrombocytopenia with severe cases; 4) increase in alternative infections arising from the anti-inflammatory response to ibrutinib and other BTKi. A small study examining the response of CLL patients on ibrutinib vaccinated against influenza A demonstrated protective titers in up to 74% of patients⁴⁶. In a prospective study performed by our own group in early stage CLL not requiring therapy, ibrutinib was administered concurrently with prenar-13 vaccine and compared to sequential prevnar 13 followed by ibrutinib. In the concurrent arm, 15/16 patients showed a significant increase in antibody titer following vaccination whereas in the sequential arm 3/13 patients had an increase in antibody titer. Additionally, long-term treatment with both ibrutinib and acalabrutinib does not significantly impair humoral function and results in elevated serum IgA levels among non-heavily pretreated patients^{47,48}. This trial will include monitoring of IgM and IgG response to SARS-CoV2 among recovering patients as one of the secondary endpoints to assure diminished response is not noted. With short exposure to ibrutinib (14 days for most), we do not anticipate this will occur and believe the risk population justifies this inclusion. While cardiac toxicity consisting predominately of hypertension or atrial fibrillation and much lesser frequency of ventricular tachycardia and rare cardiomyopathy⁴⁹⁻⁵². The risk of atrial fibrillation is approximately 3-10% and occurs over an extended period of time. Prolongation of QT is uncommon with ibrutinib. To minimize risk we will exclude patients with recent myocardial infarct, symptomatic congestive heart failure, and also poorly controlled or patients at high risk for ventricular arrhythmias. Patients with COVID-19 are in the hospital and can be closely monitored for both arrhythmia and functional cardiac problems. Given the short period of ibrutinib treatment (14 days for most), the cardiac risks seem justifiable given the high mortality associated with hospitalized COVID-19 patients with cancer. While serious bleeding has uncommonly been observed with ibrutinib therapy⁵³⁻⁵⁵, efforts to risk mitigate this by pausing therapy for surgical procedures and also avoiding anticoagulation with warfarin and other agents has greatly diminished this risk. The pathology of lung and organ failure in COVID-19 syndrome can involve microthrombi that ibrutinib may have some protective effect against. Indeed, a collective experience by our group at OSU with ibrutinib demonstrated that CLL patients had a very low level of venous or arterial thrombosis as compared to historical controls⁵⁶. To mitigate risk of serious CNS bleeding we will exclude patients with recent stroke (hemorrhagic), congenital or acquired bleeding diathesis. Patients will be monitored for bleeding and if excessive events are noted the study will be put on hold and re-evaluated. Finally, the concern for secondary infection with ibrutinib must be considered in the context of significant clinical experience with this agent in different lymphoid malignancies where over time the frequency of infections significantly diminishes. However, heavily pre-treated patients and those who have received steroids concurrently are probably more at risk^{57,58}. Given the short duration of ibrutinib in this trial (14 days for most patients), we do not anticipate that the risk of such infections will be high. We will monitor for these and adjust the trial if observed.

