9.2. Definition of an Adverse Event (AE)

An AE is any unfavorable and unintended sign, symptom, or disease temporally associated with the use of an investigational medicinal product (IMP) or other protocol-imposed

intervention regardless of attribution. The event does not necessarily have a causal relationship with that treatment or usage.

This includes the following:

- An exacerbation or an unexpected increase in frequency or intensity of a pre-existing condition (other than condition under investigation) including intermittent or episodic conditions.
- Significant or unexpected worsening or exacerbation of the condition/indication under investigation.
- A suspected drug interaction.
- An intercurrent illness.
- Any clinically significant laboratory abnormality.

An AE does not include:

- Anticipated day-to-day fluctuations of any pre-existing conditions including the disease under study.
- Signs and symptoms of the disease under study that do not represent a significant worsening or exacerbation.
- Expected progression of the disease under investigation.

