Design and Sample Size: Based on a study in China, we assume that the event rate is 40% with standard care and that the event rate can be reduced to 15% when Ibrutinib is added to standard care for COVID-19. With 60 patients and using a standard group sequential design, there is 82.8% power to detect a reduction in the event rate under the alternative hypothesis and constraining the one-sided type I error to 20%. Power was calculated using a z-test for the difference in two proportions, pooled variance, and adjustment for small sample sizes with the Casagrande-Pike-Smith correction (EAST v6.5; Cytel, Inc). There will be an interim analysis when 50% of randomized patients have been followed for 30 days from registration. The study will be stopped early if at the interim analysis the observed event rate is higher in the ibrutinib arm (Arm A) than in the control arm (Arm B). We will plan to over-accrue by about 10% for a total accrual goal of 66 patients.

Although the actual reduction in the event rate could be larger than 25%, it could also be as low as 20% and still be quite meaningful. Furthermore, there is uncertainty in the event rate of the control arm. For these reasons, we have incorporated increased flexibility at the time of the interim analysis to potentially increase the sample size if conditional power indicates promising results, and will thus implement an adaptive group sequential design (Chen, DeMets, Lan; 2004).

At the interim analysis, there are 4 possible outcomes: 1) the futility criteria are met and the trial stops early; 2) the conditional power is unfavorable ($<50\%$), and enrollment continues to the planned sample size without an increase in sample size; 3) the conditional power is in a promising zone (defined as conditional power $\geq 50\%$ and $< 82.8\%$), and sample size may be re-estimated with the original sample size updated to boost the power to a target of 82.8%, subject to a maximum sample size of 120; or 4) the conditional power is favorable ($\geq 82.8\%$), and enrollment continues to the planned

sample size without an increase in sample size. When using this procedure, no adjustment to the final test statistic or critical value from the original design is required to control the Type I error rate. In addition, if the conditional power is in the promising zone, we can choose not to increase the sample size beyond what was originally planned or by a flexible amount without penalty.

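### The interim suspension rule counts hemorrhage only inside a pool of all-cause grade 3/4 events, so if COVID-19 respiratory failure enters that pool the assumed benefit offsets a bleeding excess

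*Combined protocol and SAP*

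**What the plan says.** Section 4.5 names bleeding among the concerns with ibrutinib in this setting and commits to act on it: "Patients will be monitored for bleeding and if excessive events are noted the study will be put on hold and re-evaluated". It does not say what counts as excessive.

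Section 13 (Adverse Event Stopping Rules) sets out a plan for "comparing toxicity at the interim analyses (first 30 patients across both arms"). Accrual is suspended temporarily, and the data discussed, if any of three criteria is met. The first is "If the percentage of grade 3/4 all-cause adverse events is at least 15% higher in the ibrutinib arm", with control as the comparator; grade 2 hemorrhage judged significant is added to that same count. The second applies the same margin to all-cause grade 4 events. The third concerns treatment-related grade 5 events, with a 5% margin. None looks at hemorrhage alone.

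Whether COVID-19 deterioration is an adverse event is not settled. Section 9.2 includes "Significant or unexpected worsening or exacerbation of the condition/indication under investigation" and excludes "Expected progression of the disease under investigation". Section 9.3 leaves progression of COVID-19 out of serious adverse events.

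For the primary endpoint of respiratory failure or death, the design paragraph of Section 13 takes 40% as the control rate and supposes "the event rate can be reduced to 15% when Ibrutinib is added to standard care for COVID-19".

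**The concern.** An all-cause count in patients hospitalized with COVID-19 can take in respiratory failure, which is also the main component of the efficacy endpoint. If it does, and the drug works as assumed, the ibrutinib arm enters the toxicity comparison up to 25 points lower (40% − 15%). An equal excess of bleeding then leaves the pooled difference near zero, well short of the 15-point margin. The rule would be least sensitive to bleeding in the scenario for which the trial is sized, and the hold promised in Section 4.5 would have no numerical comparison behind it.

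The lead-in treats hemorrhage differently. Section 13 makes grade 3 or higher hemorrhage a dose-limiting toxicity in its own right, whatever the attribution. That separate view is lost once a control arm makes a comparison possible.

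**Working it through.** **The plan's own figures.** The documents give no operating characteristics for the suspension rule, so I checked the setup against neighbouring figures. A pooled-variance z-test with 30 per arm, one-sided 0.20, the Casagrande-Pike-Smith correction and the interim futility stop gives 84.2% power, against 82.8% stated. The exact probability at 15 per arm that the ibrutinib event rate exceeds control is 3.5%, 5.0%, 7.7% and 9.2% for scenarios 1–4, against 3.5%, 5.0%, 8.0% and 9.0% in the plan's table. Fifteen per arm at the interim is therefore the right basis.

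**Inputs from the documents.** 30 patients, 1:1, so 15 per arm; a margin of 15%; primary event rates r of 40% (control) and 15% (ibrutinib).

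**Assumptions.** The margin means percentage points of patients with at least one event. Since 2/15 = 13.3% and 3/15 = 20%, it takes an excess of 3 patients. The documents give no bleeding rates for this population, so b is varied. Other grade 3/4 events o run from 0 to 40%, equal in both arms. A share s of primary events enters the count: 1, ½ or 0. The three sources are independent.

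**Formulas.** Patient-level rate per arm: p = 1 − (1 − s·r)(1 − o)(1 − b). Trigger probability: the sum over i − j ≥ 3 of Bin(i; 15, p_ibrutinib) × Bin(j; 15, p_control).

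**One case by hand.** With s = 1, o = 0 and bleeding 20% vs 0%:
- Ibrutinib: 1 − 0.85 × 0.80 = 32%.
- Control: 40%.
- The ibrutinib arm is still 8 points lower despite a 20-point bleeding excess. P(trigger) = 7.9%.
- Hemorrhage alone: 1 − (0.035 + 0.132 + 0.231) = 60%.

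**Results for the first criterion, o from 0 to 40%:**

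| Bleeding, ibrutinib vs control | All primary events count | Half count | None count | Hemorrhage alone |
|---|---|---|---|---|
| 10% vs 0% | 2–7% | 8–15% | 18–29% | 18% |
| 20% vs 0% | 8–11% | 24–25% | 40–60% | 60% |
| 30% vs 0% | 17–19% | 34–47% | 53–87% | 87% |
| 35% vs 5% | 18–21% | 35–48% | 53–84% | 84% |

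**Sensitivity at 20% vs 0%, all primary events counted.**
- Under scenarios 2–4 of the plan's table: 7–14%.
- With no overlap between bleeding and primary events (o = 0): 11%.
- If the margin is read as relative rather than in points (o = 0): 25%.
- If ibrutinib has no benefit (40% in both arms): 29–40%. In that case the pooled criterion also triggers 17–18% of the time with no bleeding excess at all.

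**False alarms for a hemorrhage-only line, per look.** 2% if bleeding is 5% in both arms, and 6% if it is 10%.

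**The case against.** The strongest objection is that the masking depends on a reading the documents do not settle. A reader might infer that most grade 3/4 events will be COVID-19 respiratory failure. No section gives the mix of events, Sections 9.2 and 9.3 partly exclude disease progression, and the primary endpoint includes deaths, which are grade 5 and outside the grade 3/4 count. The column in which all primary events count is therefore the upper end of the masking. With none counted, masking largely disappears. This stands, and is why the result is given as a range. It also means the rule's sensitivity turns on a definition the plan leaves open.

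Second, other safeguards exist. Section 9.9 has the DSMC review serious adverse events in real time and safety data periodically. Section 9.5 makes major hemorrhage an event of special interest reported within 24 hours. One excess treatment-related death in 15 (6.7%) meets the grade 5 criterion. The study team may suspend accrual outside the rules. So patients after the first 30 are not unmonitored, and the Section 4.5 hold is not tied to this rule alone. All of that stands. But none of these compares bleeding between arms against a threshold, and Section 7.1.2 keeps study personnel blinded to assignment.

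Third, bleeding of 20% or more is an assumption, and Section 4.5 describes serious bleeding as uncommon. At 10% vs 0% even a hemorrhage-only line triggers only 18% of the time. A separate line improves detection of large excesses; with 15 per arm it cannot reliably find small ones.

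**Conclusion.** The point holds as a conditional one. Hemorrhage has no comparison of its own, and if COVID-19 respiratory failure enters the pooled count, the assumed benefit offsets a bleeding excess. At 20% vs 0% the first criterion triggers in 8–11%, 24–25% or 40–60% of trials as all, half or none of the primary events count, against about 60% for hemorrhage alone. This rests on 15 per arm, the margin read as points of patients, independence, assumed bleeding rates and the design effect of 40% vs 15%. The grade 4 criterion was not modelled; it pools in the same way but could add some triggers.

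A reader might go further and conclude that the rule is blind to bleeding or almost never triggers. The figures do not support that: with every primary event counted, an excess of 30 points triggers it in roughly one trial in five, and without a treatment benefit the offset disappears. The rule is insensitive under one open reading, not inoperative.

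**What to change.** In Section 13:

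1. Compare between arms, on its own line and at the plan's existing margin, the proportion of patients with hemorrhage (grade 3 or higher, or the significant grade 2 events the plan already counts).
2. Keep primary-endpoint respiratory failure out of the toxicity count and show it to the DSMC separately.
3. State whether the margin is in percentage points or relative, and whether it counts patients or events.
4. Reconcile Sections 4.5, 9.2, 9.3 and 13, so that the promised hold refers to a defined comparison and the status of COVID-19 progression is the same throughout.

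This needs wording and a few rows in the unblinded DSMC table, and no new data. The price is some extra temporary pauses: about 2% per look at 5% bleeding in both arms, 6% at 10%.

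Cardiac toxicity and infection by arm can be shown to the DSMC descriptively. Making them triggers costs more: a line with no true difference triggers about 6% of the time per look at a 10% rate and 12.5% at 20%. Further trigger lines or repeated looks should be added only after their combined false-alarm rate has been calculated.
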